### 4.3 Baseline Definitions

For all analyses, baseline will be defined as the most recent measurement prior to the first administration of study drug, including assessments done at the Screening visit, Unscheduled visits conducted prior to study treatment, and pre-treatment assessments done at the Enrollment (Baseline) visit.

In general, change from baseline ( $\Delta$ ) will be calculated as the value at a given time point,  $X$ , minus the baseline value:

$$\Delta = X \text{ Value} - \text{Baseline Value}$$

## 5 Analysis Populations

### 5.1 Safety Population

The Safety Analysis Set population will include all patients who received at least 1 dose of study drug.

## 6 Patient Disposition

The disposition of patients will be presented in total, including:

- Number of patients screened, including screen failures
- Number of patients enrolled into the study
- Number of patients who completed the treatment
- Number of patients who early withdrew/discontinued from the treatment
- Number of patients who completed the study
- Number of patients who early withdrew/discontinued from the study
- Number of patients that continued onto the extension study (RM-493-022)
- Number of patients in the Safety population

Specifically, the number and percentage of patients in each of the specified categories above will be presented. Percentages will not be presented for the number of patients enrolled or screened; all other percentages will be based on the number of patients in the safety population. The discontinuation reason as specified on the eCRFs will also be summarized by number and percent under ‘Early withdrawals/discontinuations’ section.

All patients’ disposition information (date of study completion/discontinuation, reason for discontinuation, date of last dose, reason for treatment discontinuation, and COVID-19 impact) will be presented in a data listing. Inclusion/exclusion data will also be presented by patients in a data listing.

## 7 Protocol Deviations

A protocol deviation occurs when a patient deviates from the protocol procedures. All protocol deviations will be presented by patient in a data listing.

### **COVID-19 Impact**

As the study started during the COVID-19 pandemic, missed/modified study visits, study procedures, and study dosing due to COVID-19 will be collected. A data listing will present any study visit, study procedure, and/or study assessment that due to COVID-19 were:

- Conducted remotely
- Modified or missed
- Out of window
- Resulted in study discontinuation
- Resulted in site closure

## 8 Demographic and Baseline Characteristics

### 8.1 Demographic and Baseline Characteristics

Demographic assessments for this study include:

- Age (years)
- Gender
- Ethnicity
- Race
- Weight at Baseline (kg)
- Height at Baseline (cm)
- Body Mass Index (BMI) at Baseline ( $\text{kg/m}^2$ )
- BMI Z-score at Baseline
- Waist Circumference at Baseline (cm)
- Gene Type (*POMC*, *PCSK1*, *LEPR*, and BBS)
- Fitzpatrick Skin Type (FST) at Baseline

Age, baseline weight, baseline height, baseline BMI, baseline BMI Z-score, and baseline waist circumference will be analyzed as a continuous variable. Gender, ethnicity, race, gene type, and baseline FST will be analyzed as categorical variables.

Demographics characteristics will be presented by patient in a data listing.

### 8.2 Medical History

History of relevant surgical events and medical conditions will be collected. Medical History will be coded according to MedDRA; the version used will be noted as a footnote in the tables and listings.

The number and percentage of patients reporting medical history will be summarized by system organ class (SOC) and preferred term (PT). SOC and PTs will be presented in descending frequency first and then alphabetically if there are ties. Each patient will contribute at most one count per summarization category. In other words, if a patient has more than one medical history event with same PT, the patient will be counted only once for that PT. Similarly, if a patient has more than one medical history event for a SOC, the patient will be counted only once in that SOC.

Medical history information will be reported by patient in a data listing. The listing will show the verbatim term (i.e., term reported by the site), the MedDRA SOC, MedDRA PT, event start date, and event end date (or ongoing). Medical history of weight loss interventions (type of intervention, start and end dates, and a summary of the outcome), historic height and weight (the 10 most recent height and weight measurements along with the date of assessment), and nutritional counseling (whether the patient completed nutritional counseling, and if so, the date and outcome) will be reported by patient in a data listing.

### **8.3 Concomitant Procedures**

Concomitant procedures for this study are defined as any surgical, therapeutic, or diagnostic procedure that a patient has performed on or after the date of enrollment. Procedures will be coded using the MedDRA. The versions used for the coding will be noted as a footnote in the tables and listings.

Concomitant procedures will be summarized in a table and will follow the same methods specified for medical history ([Section 8.2](#)). Concomitant procedure information will be reported by patient in a data listing. The listing will show the verbatim term, the MedDRA SOC, MedDRA PT, indication, event start date, and event end date (or ongoing).

### **8.4 Prior and Concomitant Medications**

Concomitant medications for this study are defined as any medication the patient is receiving at the time of enrollment, or any new medication received by the patient after the date of enrollment. Prior medications are medications with a stop date prior to date of study enrollment. Medications will be coded using the WHO Drug Dictionary. The versions used for the coding will be noted as a footnote in the tables and listings.

The number and percentage of patients who receive prior and concomitant medications will be summarized, separately, by the WHO Drug Dictionary Anatomical Therapeutic Chemical 4th level (ATC-4) and the preferred name. If the 4th level term is not available, the next available level (e.g., ATC-3) will be used.

ATC-4 and preferred name will be presented in descending frequency first and then alphabetically if there are ties. Each patient will contribute at most one count per summarization category. In other words, if a patient has more than one medication with same preferred name, the patient will be counted only once for that preferred name. Similarly, if a patient has more than one medication for an ATC-4 level, the patient will be counted only once in that ATC-4 level and preferred name.

Prior and concomitant medications will be presented by patient in a data listing. The listing will show the verbatim medication/therapy, the ATC-4 term, preferred name, indication, medication start date, medication end date (or ongoing), dose, dose unit, frequency, and route.

## 8.5 Physical Examination

Physical examination assessments will be presented by patient in data listings. The physical examination listing will show the date of examination, indicator examination was not done (if applicable), reason examination was not done, and Tanner Staging results (if applicable).

## 9 Efficacy Analysis

Efficacy analyses of weight, waist circumference, BMI, and BMI z-scores will be conducted using the data as observed (DAO) with no imputation for missing data. Additional analyses will be conducted using the last observation carried forward (LOCF) to impute any missing data.

If needed, weight and height will first be converted into kilograms and meters, respectively. Given that height and body weight are collected in triplicates at each visit, these will first be aggregated into one averaged value per visit. Visits will then be compared against the analysis visit window (described in [Section 4.2](#)) to select the appropriate averaged values prior to calculating weight, BMI, BMI z-score, and changes. If height is missing for an analysis visit, then height will be imputed using LOCF.

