### 9.2. Statistical Analyses

The primary objective is to evaluate the effect of setmelanotide on weight-related parameters measured in terms of the response rate to setmelanotide. Due to the small sample size of the trial, no statistical hypothesis testing is planned, and efficacy will be reported using descriptive statistics. The safety population, including all patients who receive at least 1 dose of setmelanotide, will be used as the primary analysis population for all the analyses.

AEs will be coded by preferred term (PT) and system organ class (SOC) using the latest version of MedDRA and summarized. All AE data will be presented in a data listing. TEAEs will be summarized, including by severity and relationship to trial drug. Serious AEs and AEs leading to early discontinuation will also be presented in data listings.

Actual values and changes from baseline for clinical laboratory test results, vital sign measurements etc. will be summarized using descriptive statistics (N, mean, standard deviation, median, minimum, and maximum). Shift tables will be generated for clinical laboratory test results. Clinical laboratory test results, vital sign measurements etc. will be presented in data listings.

The secondary objectives are to evaluate the effect of setmelanotide on additional weight-related parameters, as well as safety and tolerability. [REDACTED]

[REDACTED] No statistical hypothesis was made. The collected parameters will be summarized with appropriate descriptive statistics.

Due to the small sample size, summary statistics by genotype may be provided as appropriate.

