#### **4 General Analysis Conventions**

[Redacted text block]

[Redacted text block] Data for all patients in the clinical database will be included in the data listings. Calculated (derived) variables will be listed as appropriate.

All efficacy, safety and baseline characteristics variables will be presented using descriptive statistics and figures as appropriate. Continuous variables will be summarized using descriptive statistics (number of observations, mean, standard deviation (SD), median, minimum, and maximum). Categorical variables will be presented in frequency tables with number and percent of observations for each level. Missing counts for all variables will be presented for informational purposes only and will not be included in percentage calculations.

Study days will be calculated relative to the first injection of study drug. Day 1 will be the first day of study drug administration in the study. In data listings, the relative study day (in relation to date of first study drug administration) of all dates will be presented.

AEs, medical history events, and concomitant treatments/procedures will be coded using Medical Dictionary for Regulatory Activities (MedDRA), Version 24.0 or higher. Prior/concomitant medications will be coded using the World Health Organization (WHO) Drug Dictionary Global B3, March 2021 or higher.

Any changes from the SAP will be detailed in the Clinical Study Report (CSR).

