### 9.1 Primary Efficacy Endpoints

#### 9.1.1 Proportion of Patients with a Decrease from Baseline to 52 Weeks in BMI Z-score $\geq 0.2$

A “responder” is defined as a decrease from baseline to 52 weeks in the patient’s BMI z-score of  $\geq 0.2$ . The WHO Child Growth Standards 2007 will be used for BMI z-score. At each visit, an indicator variable will be created to identify patients that have a decrease in BMI z-score from baseline of 0.2 or more, allowing for the analysis of proportion of patients who meet the “responder” definition. The proportion and the corresponding 2-sided 95% CI using the Clopper-Pearson method will be reported for each visit. Sample SAS code to calculate the BMI z-score can be found at <https://www.who.int/tools/child-growth-standards/software>.

#### 9.1.2 Mean Percent Change in BMI from Baseline to Week 52

For the analysis of Mean percent change in BMI from baseline, percent changes in BMI from baseline over time will be summarized using descriptive statistics. Mean percent change in BMI from baseline over time will also be provided graphically. A 2-sided 95% CI with Student’s *t*-distribution will be provided for Mean percent change in BMI from baseline. In addition, patient figures showing the percent change in BMI from baseline will be created. Information on the patient’s baseline BMI will be included in the figure.

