### **9.2.2 Change in Weight**

[figure not shown]
Weight, change in weight from baseline, and percent change in weight from baseline will be summarized using descriptive statistics at each visit. This information will also be provided graphically for change in weight from baseline and percent change in weight from baseline. In addition, for each patient figures showing change in weight and percent change in weight from baseline over time will be created. Information on the patient's baseline weight, BMI, and BMI z-score will be included in the figure.

[figure not shown]

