# 11 Statistical/Analytical Issues

## 11.1 Handling of Missing Data

In general, the number of patients with missing values will be summarized and reported as appropriate in all outputs. Unless otherwise specified in the SAP, missing data will not be imputed.

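### LOCF is the only planned alternative to the as-observed analysis, so neither primary endpoint has a conservative check for children with no Week 52 value

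*SAP*

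**What the plan says.** - **Main analysis.** Weight, waist circumference, BMI and BMI z-score analyses "will be conducted using the data as observed (DAO) with no imputation for missing data" (SAP 9).
- **Alternative.** The same section adds: "Additional analyses will be conducted using the last observation carried forward (LOCF) to impute any missing data".
- **Default rule.** "Unless otherwise specified in the SAP, missing data will not be imputed" (SAP 11.1).
- **Denominator.** "Missing counts for all variables will be presented for informational purposes only and will not be included in percentage calculations" (SAP 4). Protocol 9.2, by contrast, says the safety population, meaning everyone with at least one dose, "will be used as the primary analysis population for all the analyses".
- **Height.** "If height is missing for an analysis visit, then height will be imputed using LOCF" (SAP 9). This rule is not confined to the LOCF analysis.
- **Responder endpoint.** "At each visit, an indicator variable will be created to identify patients that have a decrease in BMI z-score from baseline of 0.2 or more" (SAP 9.1.1), with a Clopper-Pearson interval per visit.
- **Raw weight.** "Weight, change in weight from baseline, and percent change in weight from baseline will be summarized using descriptive statistics at each visit" (SAP 9.2.2).
- **After stopping drug.** Protocol 5.1.4 asks for an early termination visit promptly once dosing ends. It also asks children who stop drug but stay enrolled to keep completing assessments.
- **Disease course.** Protocol 3.1 describes these obesities as worsening with time.

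Neither document states an expected dropout rate, response rate or effect size.

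**The concern.** A child who withdraws, or who has no measurement in the Week 52 window (Days 338 to 379, SAP 4.2), gets one of two treatments. As observed, the child leaves the calculation. Under LOCF, the child keeps the last recorded value. Because the termination visit is meant to follow the last dose closely, that value usually reflects treatment. It also comes from a younger child, in a disease expected to progress. An early fall in z-score of 0.2 or more can then be scored as a Week 52 response although nobody measured the child at Week 52.

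The risk is false reassurance. If the as-observed and LOCF results agree, the pair will look like evidence of robustness, yet neither asks what happens if the missing children lost the benefit. With 10 to 15 patients, one child is 1/15 = 6.7 to 1/10 = 10 percentage points of the response rate. SAP 12 applies all efficacy analyses to an interim dataset meant for a regulatory submission, and that dataset expressly includes children who discontinued early.

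**Working it through.** The plan has no figure of its own to reproduce. Dropout, response and growth values below are assumptions. N = 12 lies within the planned 10 to 15.

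**1. Responder endpoint.** Let N be treated, m missing at Week 52, r responders among the N - m observed, and k the missing children whose carried value meets the threshold.

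- As observed: r/(N - m)
- LOCF: (r + k)/N
- Missing counted as non-response: r/N

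LOCF can never be lower than non-responder counting, since k is at least 0. It exceeds the as-observed rate exactly when k/m is greater than r/(N - m), that is, when the missing children were last seen responding more often than completers.

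With N = 12, m = 2, r = 8 (95% Clopper-Pearson intervals):

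| Analysis | Result |
|---|---|
| As observed | 8/10 = 80% (44 to 97) |
| LOCF, k = 2 | 10/12 = 83% (52 to 98) |
| LOCF, k = 1 | 9/12 = 75% (43 to 95) |
| LOCF, k = 0 | 8/12 = 67% (35 to 90) |
| Non-responder counting | 8/12 = 67% (35 to 90) |

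Over N = 10, 12 and 15 with 1 to 3 missing and about 80% response in completers (rounded to whole patients), non-responder counting falls 5 to 26 points below as-observed. The extremes are 11/14 against 11/15 and 6/7 against 6/10. LOCF rises 1 to 6 points above as-observed when every carried value is a response.

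**2. Mean percent change in BMI.** Assume 10 completers average -10% and 2 children are missing.

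- As observed: -10.0%
- LOCF, both last seen at -10%: (10 x -10 + 2 x -10)/12 = -10.0%
- LOCF, both last seen at -2% (early exit): (10 x -10 + 2 x -2)/12 = -8.7%
- Both at 0% at Week 52: (10 x -10 + 2 x 0)/12 = -8.3%
- Both at +5% at Week 52: (10 x -10 + 2 x 5)/12 = -7.5%

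In the first LOCF case the agreement with as-observed is exact and uninformative. LOCF overstates the mean loss by 1.7 to 2.5 points if the two children are really at 0% or +5%.

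**3. Raw weight.** If weight is frozen at Week 20 and untreated gain is 2 to 6 kg per year, the gain left out at Week 52 is 2 x 32/52 = 1.2 kg to 6 x 32/52 = 3.7 kg. For weight, the error favours the drug in any child who keeps gaining.

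**4. Is the BMI error always favourable?** No. Take a child at 28 kg and 100 cm at baseline (BMI 28.00), and 27 kg and 101 cm at Week 8 (BMI 26.47, -5.5%), who then withdraws and is 106 cm at Week 52. With weight gain of 3 or 6 kg per year, either resumed from Week 8 or back on the former track:

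| Week 52 weight | True BMI change | LOCF minus true (points) |
|---|---|---|
| 27 + 3 x 44/52 = 29.54 kg | -6.1% | +0.6 |
| 28 + 3 = 31.0 kg | -1.5% | -4.0 |
| 27 + 6 x 44/52 = 32.08 kg | +2.0% | -7.4 |
| 28 + 6 = 34.0 kg | +8.1% | -13.5 |

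Negative differences favour the drug: three of four here, but not all.

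**5. Height carried with weight observed.** This works against the drug. At 110 cm and 5 to 9 cm growth per year, BMI is overstated by 1.4% to 2.5% if height dates from Week 44, and by 5.7% to 10.3% if it dates from Week 20.

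**The case against.** A reader might infer that LOCF cannot test the as-observed result at all and always flatters the drug. The documents do not support that. LOCF returns missing children to the denominator, so a child who left early without responding counts as a failure. That is why LOCF gives 67% or 75% against 80% when none or one of the two had responded.

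A reader might also take the raw-weight distortion as the size of the problem. Raw weight change is not an endpoint in Protocol Table 2; it appears only as a summary under the SAP's secondary heading. For percent BMI the error has mixed sign under assumed growth. BMI z-score is already standardised for age and sex, so the growth argument does not carry over directly. The SAP does not say whether z-score itself is carried, or BMI is carried and z-score recomputed at the Week 52 age.

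Other points also stand:

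- Children who stop drug but stay enrolled should supply off-drug Week 52 values, and Protocol 6.3 asks sites to keep them attending. The exposure is limited to children who withdraw or miss the window.
- The carried value is not certain to be on drug, since Protocol 5.1.4 allows for a termination visit four weeks or more after the last dose.
- As-observed is the main analysis, no hypothesis is tested, and missing counts, listings and individual patient figures will show each dropout.

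These points narrow the concern. They do not supply an analysis in which a missing child counts as a failure.

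**Conclusion.** The concern holds in this form: the readable plan has no conservative missing-data analysis for either primary endpoint, and LOCF is a weak, mostly non-conservative substitute. In the illustration the missing analysis would read 67% beside an as-observed 80%, and -8.3% beside -10.0%. These figures rest on assumed dropout and response. With no missing Week 52 values the issue disappears.

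Return to baseline is a plain reference point, not a worst case; at +5% for the two missing children the mean would be -7.5%. Part of SAP 4 is redacted, so the statement that LOCF is the only alternative applies to the readable text, but SAP 11.1 is readable and supports it. This is a gap in the supportive analyses and does not invalidate the main one.

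**What to change.** Keep as-observed as the main analysis. In SAP 9, add:

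1. A responder analysis over all treated patients that counts a missing Week 52 BMI z-score as non-response, with its Clopper-Pearson interval. State that this overrides the SAP 4 rule on percentages, so that it matches the protocol's analysis population.
2. A percent-BMI analysis that sets a missing Week 52 value to baseline (0% change).

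Neither needs a growth model. If LOCF is kept, do not apply it to raw weight, state whether z-score or BMI is carried, and label it non-conservative.

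The cost is SAP wording and one or two extra supportive tables. The downside is that a supportive figure may look less favourable than the main result.

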### 9.1 Primary Efficacy Endpoints

#### 9.1.1 Proportion of Patients with a Decrease from Baseline to 52 Weeks in BMI Z-score $\geq 0.2$

A “responder” is defined as a decrease from baseline to 52 weeks in the patient’s BMI z-score of  $\geq 0.2$ . The WHO Child Growth Standards 2007 will be used for BMI z-score. At each visit, an indicator variable will be created to identify patients that have a decrease in BMI z-score from baseline of 0.2 or more, allowing for the analysis of proportion of patients who meet the “responder” definition. The proportion and the corresponding 2-sided 95% CI using the Clopper-Pearson method will be reported for each visit. Sample SAS code to calculate the BMI z-score can be found at <https://www.who.int/tools/child-growth-standards/software>.

#### 9.1.2 Mean Percent Change in BMI from Baseline to Week 52

For the analysis of Mean percent change in BMI from baseline, percent changes in BMI from baseline over time will be summarized using descriptive statistics. Mean percent change in BMI from baseline over time will also be provided graphically. A 2-sided 95% CI with Student’s *t*-distribution will be provided for Mean percent change in BMI from baseline. In addition, patient figures showing the percent change in BMI from baseline will be created. Information on the patient’s baseline BMI will be included in the figure.

## **9.2 Secondary Efficacy Endpoints**

### **9.2.1 Change in BMI Percentage of the 95th Percentile**

For each patient and visit, the BMI for that patient relative to the 95th percentile for the corresponding age and gender will be calculated. The actual relative value, change from baseline in the relative value, and percent change in relative value from baseline will be summarized using descriptive statistics at each visit.

